## 5 CRITERIA FOR EVALUATION

### 5.1 Primary Endpoint

The primary endpoints for each of the primary aims are:

**Primary Aim 1:** change in fasting glucose levels relative to baseline between the intervention and control arms.

**Primary Aim 2:** change in fasting C-peptide, insulin, IGF-1, IGF-BP3, and adiponectin levels relative to baseline between the intervention and control arms.

**Primary Aim 3:** change in expression of IR, IGF-1R, and AKT on prostate cancer epithelial cells from follow-up surveillance biopsy (6 months post-randomization) relative to 'baseline' (biopsy ~6 months prior to randomization).

**Primary Aim 4:** will test whether PCa patients randomized to the intervention arm are able to sustain the beneficial changes in weight and glucose regulation an additional 6 months after the active intervention.

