## 7.5 Clinical Assessments

Study visits will occur at baseline, 3, 6 and 12 months. During study visits, participants will undergo anthropometrics, fasting blood studies and/or complete physical activity, food diaries and HRQOL questionnaires. Assessments at 6 months will be used to evaluate the effectiveness of the intervention, and at 12 months will evaluate maintenance of the intervention.

Anthropometric Measurements. Height will be measured at baseline only, and weight, waist (1" above umbilicus), hip circumferences will be measured at baseline, 3, 6 and 12 months. Dual x-ray absorptiometry (DXA) using a GE Lunar iDXA will be obtained to measure overall percent body fat, lean mass and total bone density at baseline and 12 months.

Twelve-hour fasting blood. Fasting blood samples will be collected at baseline, and at 3, 6, and 12 months. Vacutainers will be labeled with participants' study ID and date, processed within 1 hour of collection and stored at -70°C.

Prostate Tissue. As part of the consent to participate in this study, participants are asked to give permission to investigators to allow a) the collection of two extra prostate biopsy cores during their standard-of-care biopsy (UW and VA participants only), and b) access to pathology tissue from a pre-study biopsy (that was already collected as part of routine medical care for diagnostic purposes) to be used for this study (UW and VA participants only). For VA patients, separate consent allowing the collection of extra biopsy cores during a standard-of-care biopsy, and allowing access to biopsy tissue after used for diagnostic purposes will be obtained at the VAPSHCS by VA study staff on the day of their scheduled biopsy. For participants who are not patients at UW or the VA, since the collection of extra biopsy cores is not possible, they will be asked to sign a separate "Release of Information" allowing access to prostate biopsy tissue collected as part of their routine care. Tissue blocks, fixed in formalin and embedded in paraffin (standard for AS biopsies), will be sent to [name] laboratory. Participants will be enrolled on study so that the intervention calendar coincides with routine clinical care; no extra biopsies will take place outside of the routine clinical care. Tissue blocks will be cut and sections mounted on charged slides.

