### 11.1 Sample Size and Randomization

Our power calculations give the minimally detectable intervention effects for endpoints in Primary Specific Aims, setting two-sided alpha error at 5% and power at 80%. We have set a sample size of 100 in each of the intervention and control arms, based both on our overall evaluation of minimum detectable differences across the range of study endpoints and on a reasonable estimate of the number of men we can recruit. The sample size allows for a drop-out rate of 5%, and power calculations assume correlations of 0.70 between baseline and follow-up measures.

Table 4 gives the minimally detectable differences between treatment arms for serum and tissue biomarkers of glucose regulation. We have used a variety of data sources to complete these tables, attempting whenever possible to use data generated from human studies. For serum biomarkers of glucose regulation, we use data from our own pilot study and the PCPT, and for tissue expression of IR/IGF-R1 and AKT we use data from Cox et al. The minimum detectable intervention effects range from 5.3% for serum glucose to 33.1% for insulin. Previous studies have shown that dietary change can induce the following intervention effects: 7% for fasting glucose, 40% for insulin and 2.2 % for adiponectin. Our pilot study based on the DPP demonstrated an intervention effect of ↑9.7% for IGFBP3, ↓38% for insulin and ↓14% for C-peptide. Based on these observations, we will have good power to detect changes in all serum biomarkers of glucose regulation, consistent with those seen in other human intervention studies.

For expression of IR, IGF-1R and AKT on surveillance prostate biopsies, the minimum detectable intervention effects are 29.2%, 46.3% and 26.5%, respectively. Previous experimental studies in animals have

**Table 4. Minimal detectable differences in serum and tissue biomarkers at 80% power,  $\alpha=0.05$  given a sample size of 200 (100 in each of the lifestyle intervention and control arms)**

Biomarker	Baseline Mean (SD) or n (%)	Minimum Detectable Difference (MDD)	
		Mean	% of mean
Primary Aim 1 - Serum			
Fasting glucose, mg/dL	106.3 (12.6)	5.6	5.3%
Primary Aim 2 - Serum			
C-peptide, ng/mL	1.7 (1.2)	0.54	31.6%
Insulin, pmol/L	138.0 (102.0)	45.7	33.1%
IGF-1, ng/mL	232.7 (75.4)	33.8	14.5%
IGF-BP3, ng/mL	4317.6 (975.2)	436.5	10.1%
Adiponectin, ug/mL	6.1(3.9)	1.8	29.0%
Primary Aim 3 – Tissue			

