Insulin receptor	30 (34)	13.9	29.2%
IGF-1 receptor	112 (80)	32.7	46.3%
AKT	128 (83)	33.9	26.5%

shown the following results: a low-fat/low-carbohydrate diet can reduce expression of IR; low-fat, or caloric restriction diets can reduce expression of IGF-1R by 40%; and low-fat and/or low-carbohydrate and no carbohydrate diets reduce expression of AKT by up to 60%. Based on these observations, we have very good power to detect changes in IR, IGF-1R and AKT expression on epithelial cells from PCa biopsies.

Table 5 indicates the minimal detectable differences in change, and the power to detect a 5-point change between arms for each QOL tool. For most HRQOL assessments, we have good power to detect the designated minimally important differences (5-points) in QOL scores. Analyses of the association between the intervention and adverse pathology are exploratory in nature; thus, power is limited for this endpoint. Based on our clinical experience, approximately 25% of patients have 'adverse pathology' on their follow-up biopsy. Given the sample size in this study, we will be able to detect a 15% difference between intervention and control arms in the proportion of participants with adverse pathology on follow-up biopsy.

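### The Table 4 tissue detectable differences allow only for 5% drop-out, not for unusable biopsy pairs, and the very-good-power claim is unsupported for the insulin receptor

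*Combined protocol and SAP*

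**What the plan says.** Section 11.1 sets out the power calculation as "setting two-sided alpha error at 5% and power at 80" per cent, and adds: "We have set a sample size of 100 in each of the intervention and control arms". On losses it says only: "The sample size allows for a drop-out rate of 5" per cent. It also says that "power calculations assume correlations of 0.70 between baseline and follow-up measures".

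Table 4, headed "Minimal detectable differences in serum and tissue biomarkers at 80% power", puts serum and tissue markers under one caption for 200 men. Its tissue rows, as mean (SD) and MDD, are:

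- IR: 30 (34), MDD 13.9, printed as 29.2% of the mean
- IGF-1R: 112 (80), MDD 32.7, printed as 46.3%
- AKT: 128 (83), MDD 33.9, printed as 26.5%

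The text of section 11.1 repeats these three percentages in the same order. It then compares them with animal diet studies: a 40% reduction for IGF-1R, up to 60% for AKT, and a reduction of unstated size for IR. From this it concludes that "we have very good power to detect changes in IR, IGF-1R and AKT expression on epithelial cells from PCa biopsies".

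The Aim 3 endpoint in section 5.1 is the change in expression "on prostate cancer epithelial cells from follow-up surveillance biopsy" relative to a biopsy taken before the study. Section 7.5 (Prostate Tissue) offers two extra cores to UW and VA participants only. VA men give a separate tissue consent on the day of biopsy. Men from elsewhere, "since the collection of extra biopsy cores is not possible", are asked to sign a release for tissue from their routine biopsies.

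**The concern.** A man contributes to Aim 3 only if cancer cells can be scored on both his pre-study biopsy and his follow-up biopsy. Either biopsy may contain no cancer, a block may be unavailable, or a consent or release may be refused. The plan allows for none of these, so fewer than 95 pairs per arm should be expected.

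Two things are at stake. First, the tissue MDDs of a primary aim, and the confident power statement built on them, may be too favourable. Second, whether cancer appears on the follow-up biopsy is known only after randomisation, and the trial's hypothesis is that the intervention affects tumour growth. Men with paired tissue are therefore a selected subset of those randomised, and the plan does not say so.

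**Working it through.** **Inputs.** From section 11.1: two-sided alpha 0.05, power 80%, 100 per arm, 5% drop-out (100 × 0.95 = 95), correlation r = 0.70. From Table 4: the means and SDs above. From section 11, Primary Aim 3: a two-sample t-test (or Wilcoxon). The evaluable fraction is not in the documents; 80%, 70%, 60% and 50% of the 95 are assumed.

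**Formulas.** MDD = d(n) × SD of change, where d(n) is the standardised difference giving 80% power in a two-sample t-test (noncentral t). SD of change = SD × √(2(1 − r)). This equals the raw SD at r = 0.5 and 0.775 × SD at r = 0.70.

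**Reproducing Table 4.** d(95) = 0.4086. With the raw SD:

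- IR: 0.4086 × 34 = 13.9
- IGF-1R: 0.4086 × 80 = 32.7
- AKT: 0.4086 × 83 = 33.9

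All three match. With r = 0.70 and 95 per arm the results are 10.8, 25.3 and 26.3. With the raw SD and 100 per arm they are 13.5, 31.9 and 33.1. Neither set matches.

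**Percentages.** 13.9/30 = 46.3% (IR), 32.7/112 = 29.2% (IGF-1R), 33.9/128 = 26.5% (AKT). The IR and IGF-1R figures are swapped in both Table 4 and the text. As printed, the IGF-1R MDD (46.3%) exceeds the cited 40% effect; corrected (29.2%), it does not.

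**Fewer evaluable pairs, Table 4's own SD.** MDDs are in the order IR / IGF-1R / AKT.

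| Evaluable | n per arm | d(n) | MDD | % of mean | Power at printed MDDs | Power, 40% IGF-1R effect |
|---|---|---|---|---|---|---|
| 100% | 95 | 0.409 | 13.9 / 32.7 / 33.9 | 46.3 / 29.2 / 26.5 | 80% | 97% |
| 80% | 76 | 0.457 | 15.6 / 36.6 / 38.0 | 51.8 / 32.7 / 29.7 | 71% | 93% |
| 70% | 66.5 | 0.490 | 16.6 / 39.2 / 40.6 | 55.5 / 35.0 / 31.7 | 65% | 89% |
| 60% | 57 | 0.529 | 18.0 / 42.3 / 43.9 | 60.0 / 37.8 / 34.3 | 58% | 84% |
| 50% | 47.5 | 0.581 | 19.8 / 46.5 / 48.2 | 65.8 / 41.5 / 37.7 | 50% | 77% |

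The 40% IGF-1R effect is 0.40 × 112 = 44.8, or 44.8/80 = 0.56 SD. It needs about 51 per arm for 80% power, so 1 − 51/95 = 46% of pairs can be lost first. The 60% AKT effect is 76.8, or 76.8/83 = 0.93 SD, and still has 99% power at 50% evaluable.

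**If r = 0.70 holds.** At 76 per arm the MDDs are 12.0 / 28.3 / 29.4, below those printed. At 57 per arm they are 13.9 / 32.8 / 34.0, within 0.1 of those printed.

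**IR with no tissue loss.** The documents give no IR effect to test against the 46.3% MDD. Purely as an illustration, an assumed 40% reduction (12 units) has 68% power at 95 per arm with the raw SD and 88% with r = 0.70.

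**The case against.** The strongest defence is the stated correlation. If r = 0.70 applies to tissue, the printed MDDs already have room for about 40% tissue loss, and the power statement is safe for IGF-1R and AKT against the plan's own benchmarks. Even without 0.70, IGF-1R keeps 80% power until nearly half the pairs are gone, and AKT well beyond that. This stands, and it limits the point. It does not close it. Table 4 does not use 0.70 at its own sample size, and nothing in section 11.1 says that the difference was meant as an allowance for tissue.

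Several stronger readings are tempting but are not supported:

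- *The plan calls Aim 3 intention-to-treat.* A reader might infer this from the sentence covering all analyses. That sentence sits under Aim 1 in section 11 and is carried to Aim 2. The synopsis places it in the block for Aims 1 and 2. Aim 3 has no such statement; it simply names no analysis set.
- *The tissue rows use the same 95 men as the blood tests.* With 95 per arm and the raw SD, the glucose MDD would be 0.4086 × 12.6 = 5.1 and insulin 0.4086 × 102 = 41.7, against the printed 5.6 and 45.7. The serum rows need a correlation of 0.40, or about 79 per arm, so the shared basis is not established.
- *The men were chosen for low-volume disease, so negative biopsies will be common.* Section 6.2 limits stage, Gleason score and PSA. It sets no limit on cores or volume.
- *Men outside UW and VA supply no tissue.* They lack the extra cores, but their routine biopsy tissue can be obtained by release. Access is reduced, not absent.
- *Men without cancer on follow-up should be given the lowest rank.* This is a debatable choice, since it treats absent tissue as the greatest receptor reduction when the biopsy may have missed the tumour. It is not a required change.

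**Conclusion.** The concern holds in a limited form. The tissue MDDs rest on 95 per arm and carry no loss beyond drop-out, although the endpoint and tissue access make further loss likely. The direction of the error is clear only with the SD that Table 4 actually used. Its size is unknown, because every evaluable fraction above is an assumption. Across 80% to 50% evaluable, the MDDs rise by 12% (0.457/0.409) to 42% (0.581/0.409). The documents do not show that the trial is underpowered for the cited IGF-1R or AKT effects.

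Two findings need no assumption about tissue. The IR and IGF-1R percentages are swapped. And the power claim has no basis for IR, where no effect size is cited.

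**What to change.** In section 11.1 and Table 4:

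1. Recompute the tissue rows over a stated range of expected evaluable pairs per arm, naming the correlation actually used, and reconcile it with the stated 0.70.
2. Correct the percentages to 46.3% for IR and 29.2% for IGF-1R, in both table and text.
3. Remove the very-good-power statement for IR. For IGF-1R and AKT, tie it to the cited effect and to the number of pairs it needs.

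In section 11, Primary Aim 3, describe the analysis as a comparison among men with paired scorable tissue, and commit to reporting the evaluable share by arm, because cancer on the follow-up biopsy is a post-randomisation condition.

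The cost is wording and a short recalculation, with no new data. The downside is that the stated MDDs will look less favourable if the raw SD is kept.

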## 12 DATA COLLECTION, RETENTION AND CLINICAL MONITORING

### 12.1 Data Collection Instruments

The Investigator will prepare and maintain adequate and accurate source documents designed to record all observations and other pertinent data for each subject who signs consent or treated with the study intervention or enrolled in the study.

Study personnel will enter data from source documents corresponding to a subject's visit into the protocol-specific electronic study forms OR study database when the information corresponding to that visit is available. Subjects will not be identified by name in the study database or on any study documents to be collected, but will be identified by a site number, subject number and initials.

The study staff is responsible for all information collected on subjects enrolled in this study. All data collected during the course of this study must be reviewed and verified for completeness and accuracy by the study staff. A copy of the CRF will remain in the study's files at the completion of the study.

### 12.2 Data Management Procedures

For this proposal we will adhere to all federal requirements to submit relevant publications to PubMed Central. We will present results from this study at national and international scientific meetings. We will collaborate with other investigators, both within and external to FHCRC to share data and knowledge as required by the NIH. For outside investigators wishing to use the data generated from this study, we will supply de-identified data. These data will be available approximately 12 months after the close of the intervention and after the submission of the primary manuscripts from this study. The costs for data transfer, including generation of data dictionaries and other documentation will be the responsibility of the investigator requesting to use the data. We are cognizant of and completely support the need to share data and resources with other investigators to maximize the NIH investment and prevent duplication of efforts. We welcome collaborations with outside investigators and those wishing to collaborate and use data will be asked to contact [name] directly.

### 12.3 Archival of Data

Databases are maintained with nightly backups and security updates.

### 12.4 Availability and Retention of Investigational Records

The study staff must make study data accessible to the IRB upon request. A file for each subject must be maintained that includes the signed Informed Consent, HIPAA Authorization and Assent Form and copies of all source documentation related to that subject. The study staff must ensure the reliability and availability of source documents from which the information on the CRF was derived.

**Table 5. Power and MDD for QOL**

QOL tool	Baseline Mean (SD)	Mean MDD	Power to detect
			5-point difference in score
MAX-PC	14 (9) 	4.0	97%
EQ-5D	86 (15) 	6.7	63%
EPIC-Urinary bother	86 (14) 	6.3	69%
EPIC-Sexual bother	63 (23) 	10.3	32%

All study documents (e.g., patient files, signed informed consent forms, copies of CRFs, Essential Document and Study Reference Binders) must be kept secured.

## **12.5 Monitoring**

Monitoring and/or auditing of this study will be performed by Fred Hutchinson Cancer Research Center according to the Institutional Data and Safety Monitoring Plan (DSMP).

## **12.6 Subject Confidentiality**

In order to maintain subject confidentiality, only a subject number and subject initials will identify all study subjects on CRFs and other documentation submitted to the IRB.

## **12.7 Protocol Amendments**

Any amendment to the protocol will be written by the Investigator. Protocol amendments cannot be implemented without prior written IRB approval except as necessary to eliminate immediate safety hazards to patients. A protocol amendment intended to eliminate an apparent immediate hazard to patients may be implemented immediately, provided the IRB is notified within five working days.

## **12.8 Institutional Review Boards**

The protocol and consent form will be reviewed and approved by the IRB prior to study initiation. Serious adverse events regardless of causality will be reported to the IRB in accordance with the standard operating procedures and policies of the IRB, and the Investigator will keep the IRB informed as to the progress of the study. The Investigator will obtain assurance of IRB/IEC compliance with regulations.

Any documents that the IRB may need to fulfill its responsibilities (such as protocol, protocol amendments, Investigator's Brochure, consent forms, information concerning patient recruitment, payment or compensation procedures, or other pertinent information) will be submitted to the IRB/IEC. The IRB/IECs written unconditional approval of the study protocol and the informed consent form will be in the possession of the PI before the study is initiated. This approval must refer to the study by exact protocol title and number and should identify the documents reviewed and the date of review.

Protocol and/or informed consent modifications or changes may not be initiated without prior written IRB/IEC approval except when necessary to eliminate immediate hazards to the patients or when the change(s) involves only logistical or administrative aspects of the study. Such modifications will be submitted to the IRB/IEC and written verification that the modification was submitted and subsequently approved should be obtained.

The IRB/IEC must be informed of revisions to other documents originally submitted for review; serious and/or unexpected adverse experiences occurring during the study in accordance with the standard operating procedures and policies of the IRB; new information that may affect adversely the safety of the patients of the conduct of the study; an annual update and/or request for re-approval; and when the study has been completed.

## **12.9 Informed Consent Form**

Informed consent will be obtained in accordance with the Declaration of Helsinki, ICH GCP, US Code of Federal Regulations for Protection of Human Subjects the Health Insurance Portability and Accountability Act (HIPAA, if applicable), and local regulations.

A properly executed, written, informed consent will be obtained from each subject prior to entering the subject into the trial. Information should be given in both oral and written form and subjects must be given ample opportunity to inquire about details of the study. If appropriate and required by the local IRB/IEC, assent from the subject will also be obtained. If a subject is unable to sign the informed consent form (ICF) and the HIPAA authorization, a legal representative may sign for the subject. A copy of the signed consent form (and assent) will be given to the subject and the original will be maintained with the subject's records.

During the course of the study, if modifications are made to the consent form that impact the subject, the subject will be re-consented as described above.

## 12.10 Publications

The publication or presentation of any study results shall comply with all applicable privacy laws, including, but not limited to, the Health Insurance Portability and Accountability Act of 1996.

